Posaconazole for the Prevention of COVID-19 Associated Pulmonary Aspergillosis in Critically-Ill Patients: A European Multicenter Case-Control Study

(NCT05065658)

The study titled "*Posaconazole for the Prevention of COVID-19 Associated Pulmonary Aspergillosis in Critically-Ill Patients: A European Multicenter Case-Control Study*" (NCT05065658) was conducted as a sub-study within the protocol of a larger prospective, multicenter trial including amendments of the local ethic committees. The overarching trial, titled "*Pulmonary Aspergillosis in Critically Ill COVID-19 Patients in Intensive Care Units - A Multinational Explorative Trial*" provided the framework for exploring key outcomes related to pulmonary aspergillosis in critically ill COVID-19 patients. The sub-study leveraged data collected within the parent study to specifically assess the role of posaconazole in preventing COVID-19-associated pulmonary aspergillosis. This design ensured consistency and robust collaboration across the two investigations.

The study protocol of the multicenter, prospective trial "*Pulmonary Aspergillosis in Critically Ill COVID-19 Patients in Intensive Care Units - A Multinational Explorative Trial*" can be found below.

Pulmonary Aspergillosis in Critically Ill COVID19 Patients in Intensive Care Units - a multinational explorative trial

Running title:

Aspergillosis in COVID19 on ICU

Investigators

[name]	[contact]	Medical University of Graz, Austria
-----------------	-------------------------------	-------------------------------------

[name]	[contact]	Medical University of Graz, Austria University of California San Diego, USA
[name]	[contact]	LKH-Graz West, Austria
[name]	[contact]	University of Cologne, Germany
[name]	[contact]	University of Cologne, Germany
[name]	[contact]	University of Cologne, Germany
[name]	[contact]	University of Manchester, United Kingdom
[name]	[contact]	University of Manchester, United Kingdom
[name]	[contact]	University of Manchester, United Kingdom
[name]	[contact]	University of Manchester, United Kingdom
[name]	[contact]	University of Manchester, United Kingdom
[name]	[contact]	University of California San Diego, USA
[name]	[contact]	Innsbruck Medical University, Austria
[name]	[contact]	Innsbruck Medical University, Austria
[name]	[contact]	KU Leuven, Belgium
[name]	[contact]	KU Leuven, Belgium
[name]	[contact]	KU Leuven, Belgium
[name]	[contact]	University of Genoa, Italy
[name]	[contact]	University of Genoa, Italy
[name]	[contact]	University of Genoa, Italy
[name]	[contact]	Paris Diderot University, France
[name]	[contact]	Paris Diderot University. France
[name]	[contact]	Bordeaux's CHU, France
[name]	TBA	Bordeaux's CHU, France
[name]	TBA	Bordeaux's CHU, France
[name]	TBA	Bordeaux's CHU, France
[name]	TBA	Bordeaux's CHU, France
[name]	[contact]	Hospital General Universitario Gregorio Marañón, Madrid, Spain

[name]	[contact]	University Hospital South Ann Arbor, USA
[name]	[contact]	University Hospital South Ann Arbor, USA
[name]	[contact]	The Aga Khan University, Pakistan

Abstract

In December 2019, a novel coronavirus named SARS-CoV-2 spread throughout the world and is causing a global pandemic. In contrast to many other ordinary respiratory viruses, a significant proportion of patients diagnosed with SARS-CoV-2 infections need to be hospitalized or even admitted to intensive care units (ICUs). We know that patients with severe influenza infection are at a higher risk of developing invasive pulmonary aspergillosis (IPA). First reports of IPA have also emerged among SARS-CoV-2 infected patients admitted to the ICU. We hypothesize that patients with severe SARS-CoV-2 infection requiring ICU-level care are also at a higher risk of developing IPA.

The main objective of this explorative trial is to screen patients retrospectively based on routinely performed investigations for the presence of IPA. In addition, remainders of routinely performed bronchoalveolar lavage fluid (BALF) samples and endotracheal aspirates will be collected and stored for retrospective biomarker testing. Left-over blood samples (plasma, serum, and urine) will also be collected and stored for the measurement of fungal biomarkers, soluble urokinase plasminogen activator receptor and interleukins 6 and 8, as well as urine biomarkers for IPA including Triacetyl fusarine C (Innsbruck Medical University). In addition, the respiratory tract microbiome will be analyzed in a subset of patients (University of Manchester).

No procedures or interventions beyond those done as a part of routine clinical care will be performed. All tests will be performed in samples left over from clinical routine. Data will be collected in an anonymized fashion in an electronical case report form.

Background

Infections with human coronavirus are common, especially among the cold weather season. They are responsible for approximately 10 - 15% of common colds in the winter time (1). However, within the last 20 years there have been three relevant outbreaks with highly pathogenic coronavirus leading to a large number of infected patients and a significant number of deaths. The outbreak of the severe acute respiratory syndrome (SARS) coronavirus (SARS-CoV) in 2002 infected more than 8000 people in 28 countries, with a case fatality rate of 9.8% (2).

In 2012 another outbreak with a highly pathogenic coronavirus started on the Arabian Peninsula. The middle east respiratory syndrome coronavirus (MERS-CoV) has been infecting over 2400 people since 2012, with a case fatality rate of approximately 35% (3). However, none of these two highly pathogenic coronavirus infections caused a global pandemic.

In December 2019, an outbreak with a novel coronavirus started in China. The severe acute respiratory syndrome coronavirus 2 (SARS-CoV-2) has now caused a pandemic and has been infecting at least 2.8 million people in 185 countries (up to 27-APR-2020, source: WHO). As up to 27-APR-2020 more than 195 000 people around the world died due to coronavirus disease 2019 (COVID19). Although the vast majority of COVID19 cases are mild to moderate (approximately 80%), approximately 15% of patients diagnosed with COVID19 require hospitalization and supplementary oxygen, and 5% of patients develop critical disease with acute respiratory distress syndrome (ARDS) and require ICU admission and mechanical ventilation (4).

ARDS may also be a consequence of infections with other respiratory virus, like influenza. Recently, it was shown that patients with influenza-associated ARDS are at a higher risk for developing pulmonary mold infections, primarily from IPA. In large multicenter trial the prevalence of pulmonary aspergillosis among patients with influenza associated ARDS was 19% (5). As patients with influenza associated aspergillosis have a mortality rate of over 50% (5), mold active antifungal prophylaxis is a standard of care in many centers for these patients. From Wuhan, epidemiological studies indicate that invasive fungal infections may occur in between 4-5% of COVID-19 episodes requiring ICU admission (6,7). Given that in Wuhan galactomannan testing is rarely available and fungal diagnostics are sparse, this is likely an underestimate of the real burden of IPA in patients with COVID-19 requiring ICU admission.

Diagnosis of IPA is based on patients risk factors (e.g. severe influenza), imaging studies (chest X-ray, chest computed tomography) and microbiological investigations, like culture from bronchoalveolar lavage fluid (BALF), galactomannan (GM), aspergillus lateral-flow device (LFD), galactomannan lateral-flow assay (LFA), Triacetylfusarine-C (TAF-c) or aspergillus PCR (8).

The aims of this study are to determine the prevalence of IPA in COVID19 patients in the ICU and to determine the diagnostic performance of BALF fungal biomarkers for diagnosis of IPA.

The study consists of three different sub-studies:

Base module “A”: Epidemiological study (ICU patients only)

Add on Aim “B”: Biomarker study (ICU patients only)

Add on Aim “C”: Microbiota study (ICU patients and patients on general wards)

All participating centers must participate in Base module “A” plus at least one of the two add on modules (B or C or both).

Objectives

Aims “A”

Primary: Provide necessary data to interpret laboratory findings for Module B and/or C

Secondary: Determine the prevalence of IPA in patients with critical COVID19 in intensive care units

Aims “B”

The objectives of the biomarker (“B”) sub study are as following:

- 1.) Determine diagnostic performance of BALF-GM for IPA in COVID19
- 2.) Determine diagnostic performance of BALF-LFD for IPA in COVID19
- 3.) Determine diagnostic performance of BALF-LFA for IPA in COVID19
- 4.) Determine diagnostic performance of BALF Aspergillus PCR in COVID19
- 5.) Determine performance of urine biomarkers for IPA in COVID19
- 6.) Determine radiological findings on chest imaging in COVID19 patients with and without IPA
- 7.) Outcome of COVID19 patients on ICU with and without IPA
- 8.) Length of ICU stay in COVID19 patients with and without IPA
- 9.) Prognostic potential of plasma and BALF soluble urokinase plasminogen activator receptor (suPAR), IL-6, and IL-8 in COVID19 patients with and without IPA (single measurements and kinetics)

Aim “C”

The primary objective of the microbiota sub study is to determine diagnostic performance of mycobiome tests in COVID-19 patients.

Study population

There is no pre-defined upper limit of patients that may be included in this study by the participating centers. The total number of patients will depend on the course of the COVID19 pandemic within the next months.

Inclusion criteria

Inclusion criteria required for all sub studies

- 1.) Patient has PCR confirmed SARS-CoV-2 infection

Additional inclusion criteria for biomarker study “B”

- 1.) Bronchoscopy or endotracheal aspiration is performed during routine clinical work (indicated by the treating physician only - no intervention for study purpose only)
- 2.) Chest imaging (e.g. CT chest scan or chest x-ray) available +/- 7 days of bronchoscopy/endotracheal aspiration

Additional inclusion criteria for microbiota study “C”

- 1.) Bronchoscopy or endotracheal aspiration is performed during routine clinical work (indicated by the treating physician only - no intervention for study purpose only) in ICU patients **OR** patients are willing to give sputum samples if they are on general wards after signing an informed consent
- 2.) Chest imaging (e.g. CT chest scan or chest x-ray) available +/- 7 days of bronchoscopy/endotracheal aspiration

Exclusion criteria

- 1.) <18 years of age

Material, Methods and Study Period

Specimen for Biomarker Testing (Aim “B”)

Respiratory specimen from patients fulfilling the inclusion criteria (BALF or endotracheal aspirate), obtained at ICU admission and any available follow up samples obtained during the ICU stay will be collected, aliquoted (up to three aliquots each at least 1ml specimen) and stored at -80°C. In case remaining samples volume is less than 1ml, addition of sterile NaCl 0.9% is necessary to obtain at least one aliquot containing at least 1 ml of respiratory specimen. Highly viscid samples may be diluted with NaCl 0.9% to enable further work up. Liquifying agents, such as Suptasol® (=dithiothreitol) must not be used as they significantly affect results of biomarker testing, such as galactomannan. If available at the participating site, respiratory samples should be cultured on sabouraud-dextrose-agar and sent to the Innsbruck Medical University ([name]) for further analysis.

Left-over blood samples (plasma and serum) from routinely performed blood drawings at the time of the respiratory sample and during the course of ICU admission (at the day of ICU admission, followed by 1 - 3 times per week, depending on the local screening strategies), will be stored at -80°C for retrospective suPAR, IL-6, and IL-8 testing.

Urine samples will be collected 1 - 3 times a week (on same day as blood samples). Total samples volume from each visit should be 10 ml of urine. Samples should be divided in aliquots, with a total volume of 10 ml for each visit and stored at -80°C without any pretreatment.

After the recruiting phase of the study the following parameters will be tested from the obtained specimens and samples:

- 1.) Galactomannan ELISA from BALF or endotracheal aspiration and serum
- 2.) 1,3- β -D-Glucan from serum
- 3.) Aspergillus lateral-flow device from BALF or endotracheal aspiration and serum
- 4.) Galactomannan lateral-flow assay from BALF or endotracheal aspiration and serum
- 5.) Aspergillus PCR from BALF or endotracheal aspiration
- 6.) suPAR, IL-6, and IL-8 from BALF and plasma samples
- 7.) GM, triacetylfusarinine C from urine samples

In case any of these parameters are performed during routine clinical work, they will not be determined a second time from stored samples. All laboratory tests performed for study purposes will be done anonymized. Only left-over samples obtained during routine clinical work

will be collected for this study. No intervention to the patients will be performed for study purposes only.

Specimen for Mycobiome Study (Aim “C”)

In a subset of patients, lower-respiratory tract samples (BAL and endotracheal aspiration) or sputum samples from patients on ICU and sputum samples from COVID-19 patients on general wards will be collected and processed according to the attachment “Respiratory sample collection for sub-study C”.

Respiratory samples will be collected and inactivated either by adding an inactivating agent (containing >0.3% TnBP and 0.1% Triton X100 or Tween 80) or by heat inactivation by heating the samples to 65°C for 15 minutes. A sample volume of at least 0.5 ml is required, but a sample volume of >1mL would be optimal. Samples will then be stored at the participating center and sent to [name] from the University of Manchester in batches on dry ice.

Study Period

Inclusion of patients may start as soon as possible in the participating centers. The end of the study period is currently open. It will highly depend on the course of the pandemic within the next months. Patients may be included in the study until 31st-DEC-2020.

Case Report Form

For data acquisition and storage FungiScope® Registries will be used. The anonymized electronic case report form will be accessible through www.clinicalsurveys.net. ClinicalSurveys.net employs a customized version of Questback's internationally acclaimed EFS Survey® and EFS Leadership® technology to provide the user with an easy-to-use online documentation system. Following data will be obtained in the CRF:

- 1.) Date of SARS-CoV-2 diagnosis (=date of positive PCR)
- 2.) Duration of ICU stay

- 3.) Results from routinely performed microbiological investigations (BALF culture, biomarkers, etc.)
- 4.) Routine laboratory biomarkers (Galactomannan, BDG, etc.)
- 5.) Chest imaging results +/- 7 days of bronchoscopy/endotracheal aspiration
- 6.) Host factors and genetic and other risk factors for IPA
- 7.) Antifungal treatment
- 8.) Outcome data
- 9.) Cause of death (if applicable)

The FungiScope® Registries are in accordance with all applicable laws and regulations including the International Conference on Harmonization (ICH) Guideline for Good Clinical Practice (GCP) the ethical principles that have their origins in the Declaration of Helsinki (current official version: Fortaleza, 2013), and applicable privacy laws (Regulation (EU) 2016/679). All Good Epidemiological Practice (GEP) requirements are met by the registry. Users can only view and modify their own contributions. All data transmissions are encrypted via TLS 1.2 with an AES 256 GCM bit key and ECDHE RSA key exchange; certificate is provided by COMODO RSA Domain Validation Server. Data are only documented anonymously; no directly identifying data other than the investigator names and email addresses are stored on Questback servers. Administration of the eCRF is limited to selected and named administrators at the University Hospital Cologne. Any data manipulation by users and administrators is logged in an audit trail allowing complete data reconstruction. The platform has been extensively used in hundreds of surveys and studies and has received approval by the responsible data protection officers at the University Hospital Cologne.

Criteria for defining aspergillosis

Invasive aspergillosis will be classified according to the scheme published by Blot et al. (9) with some modifications:

- 1.) COVID19 requiring ICU admission was added as host factor
- 2.) Tracheal aspiration was equaled to BALF in terms of microbiological testings'
- 3.) Serum and BALF GM was added as entry criterion

The modified diagnostic criteria are displayed in table 1.

Table 1 Modified diagnostic criteria for invasive aspergillosis

Proven invasive aspergillosis	
- Idem to the EORTC/MSG criteria	
Putative invasive aspergillosis (all four criteria must be met)	
1.) Aspergillus recovery from BAL or endotracheal aspirate or positive galactomannan [either serum (>0.5 ODI) or respiratory sample (>1 ODI)]	
2.) Compatible signs and symptoms	

 - Fever refractory to at least 3 d of appropriate antibiotic therapy - Recrudescent fever after a period of defervescence of at least 48 h while still on antibiotics and without other apparent cause - Pleuritic chest pain - Pleuritic rub - Dyspnea - Hemoptysis - Worsening respiratory insufficiency in spite of appropriate antibiotic therapy and ventilatory support 	

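### Aim B1 judges BALF galactomannan against an IPA definition that the same galactomannan result can satisfy, so its specificity and PPV are partly built in

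*Protocol*

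**What the plan says.** The Background section of the protocol names two study aims. One is the prevalence of IPA; the other is to "determine the diagnostic performance of BALF fungal biomarkers for diagnosis of IPA". The first objective listed under Aims B is: "Determine diagnostic performance of BALF-GM for IPA in COVID19". No positivity cut-off is given for GM as the test under evaluation.

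The section on criteria for defining aspergillosis modifies a published scheme in three ways, the third being: "Serum and BALF GM was added as entry criterion". In Table 1, putative IPA needs all four criteria. Criterion 1 is Aspergillus recovered from BAL or endotracheal aspirate, or "positive galactomannan [either serum (>0.5 ODI) or respiratory sample (>1 ODI". Criterion 2 is a list of signs that includes dyspnea. Criterion 3 is any abnormality on chest X-ray or CT. Criterion 4a is met by COVID-19 requiring ICU admission, and Aim B is limited to ICU patients.

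Three further passages matter:

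- The Abstract bases retrospective screening for IPA on routine investigations, and the Case Report Form section records routine culture and GM.
- The section on specimens for Aim B states: "In case any of these parameters are performed during routine clinical work, they will not be determined a second time from stored samples".
- The same section plans the remaining tests for later: "After the recruiting phase of the study the following parameters will be tested from the obtained specimens and samples".

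The SAP analyses posaconazole prophylaxis and contains no diagnostic-accuracy analysis.

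**The concern.** A reference standard should be independent of the test that it judges. Here a respiratory GM above 1 ODI opens the case definition by itself. Criterion 4a then removes nobody, and criteria 2 and 3 are non-specific in patients whom the Background describes as having ARDS and needing ventilation. Where the GM result being evaluated is also the one used for classification, and the index cut-off is 1 ODI or higher, a false-positive GM is counted as false only if criterion 2 or 3 fails.

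To that extent the reported specificity and PPV describe the definition rather than the test. A poor assay and a good one would look alike, on one of the study's two stated aims. Sensitivity is distorted too, but in no fixed direction.

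**Working it through.** The plan gives no accuracy figure or target for Aim B1, so there is nothing to reproduce. The check enumerates the two-by-two table that Table 1 implies.

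**Inputs.** The classification rule is from Table 1. All accuracy values are assumptions:

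- Respiratory GM at >1 ODI: sensitivity 60%, specificity 90%.
- Culture: 50% and 97%.
- Serum GM: sensitivity 20% (varied 10-30%), specificity 97%.
- Errors are independent given disease.
- Prevalence is 10%, between the 4-5% and the 19% (influenza) quoted in the Background; results at 19% are in brackets.
- q is the share meeting criteria 2 and 3, reading criterion 2 as needing one listed sign.
- f is the share of patients whose evaluated GM enters the classification (the overlap).

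**Building blocks at 10% prevalence**

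- GM positive: 0.1×0.6 + 0.9×0.1 = 0.150. True PPV = 0.06/0.15 = 40% (58.5%).
- Culture or serum GM positive: with IPA 1 − 0.5×0.8 = 0.600; without IPA 1 − 0.97×0.97 = 0.0591.
- GM negative but entering by culture or serum: 0.1×0.4×0.600 + 0.9×0.9×0.0591 = 0.0719.
- GM positive and also entering by culture or serum: 0.06×0.600 + 0.09×0.0591 = 0.0413.

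**1. Full overlap (f = 1), cut-off 1 ODI.** PPV = 0.15q/0.15 = q, whatever the accuracy of GM. Specificity = (0.85 − 0.0719q)/(1 − 0.2219q).

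| q | Apparent specificity | Apparent PPV |
|---|---|---|
| 100% | 100% (100%) | 100% |
| 95% | 0.7817/0.7892 = 99.0% (98.7%) | 95% |
| 90% | 0.7853/0.8003 = 98.1% (97.4%) | 90% |
| 80% | 0.7925/0.8225 = 96.4% (95.0%) | 80% |

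If all patients with IPA but only 80-95% of the others meet criteria 2 and 3, PPV is (0.06 + 0.09×0.80)/0.15 = 88% to (0.06 + 0.09×0.95)/0.15 = 97% (92-98%), and specificity is 97.8-99.4%.

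**2. Partial overlap, q = 1.** GM-positive cases = 0.15f + 0.0413(1 − f). Specificity = 0.7781/(0.7781 + 0.15 − GM-positive cases). Over serum sensitivity 10-30%:

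| f | Apparent specificity | Apparent PPV |
|---|---|---|
| 0% | 87.5-88.0% (85.0-86.0%) | 26-30% (35-40%) |
| 25% | 90.3-90.7% (88.3-89.1%) | 44-47% (51-55%) |
| 50% | 93.3-93.6% (91.9-92.5%) | 63-65% (67-70%) |
| 100% | 100% (100%) | 100% (100%) |

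Apparent specificity equals the true 90% at f = 18-22% (32-37%). Below that it is too low; above it, too high.

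**3. Index cut-off below 1 ODI.** Suppose 5% of patients lie between the cut-off and 1 ODI, equally with and without IPA, with f = 1 and q = 1. Non-cases in that band are 0.1×0.05×0.4 + 0.9×0.05×0.9409 = 0.0443. Specificity = (0.7781 − 0.0443)/0.7781 = 94.3%, against a true 85%. With 2% and 10% in the band it is 97.7% and 88.6%, against 88% and 80%. At half overlap the excess falls to 1.1-3.5 points over both prevalences.

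**4. Can the design tell assays apart?** With q = 95%, true specificities of 85% and 95% appear as 98.7% and 99.4% (98.3% and 99.0%) at full overlap. At half overlap they appear as about 90% and 96% (88-89% and 94%).

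**5. Sensitivity, full overlap.** A true 60%/90% test gives 0.15/0.2219 = 67.6%; the range over serum sensitivity and both prevalences is 67-70%. A true 80%/95% test at 10% prevalence gives 66-67%. Without the serum route these become 77% and 78%. The first is above the truth and the second below it either way.

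**The case against.** The best opposing argument concerns how much overlap there will be. GM not done routinely is to be measured on stored samples after recruitment, while IPA is screened from routine investigations. Those later results may never enter the classification. At low overlap the specificity bias reverses, so figures near 100% are an upper extreme and not a forecast. This stands: the documents give neither the overlap nor the index cut-off.

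Second, the protocol does not say outright that Table 1 is the reference for Aim B1, and the SAP grades CAPA as proven, probable or possible, which are not Table 1's categories. But Table 1 is the only IPA definition set out in the text, and the SAP's grades are not defined there. A reader following the protocol would use Table 1.

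Third, the sensitivity figures depend on the assumed serum route, as step 5 shows. That limits what can be said about sensitivity. Dropping the serum route changes full-overlap specificity by at most 0.2 points and leaves PPV equal to q.

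Finally, the parent study is exploratory and states the GM modification openly. Openness about the definition does not remove the bias from an accuracy estimate based on it.

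**Conclusion.** The concern holds. Table 1 lets the index test define the case, and the rule against repeating routine GM means that one result can play both roles. With complete overlap and a cut-off of 1 ODI or higher, PPV is fixed by the share meeting criteria 2 and 3 when meeting them is independent of disease and GM; specificity is at or near 95% or above for q of 80% or more in the settings examined.

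The mechanism follows from the text; the size rests on assumed accuracies, independent errors and three quantities that the documents do not state: the index cut-off, the overlap, and the share meeting criteria 2 and 3. Specificity near 100% needs high overlap. The point concerns the first listed biomarker objective and should be changed; it does not bear on the posaconazole analysis.

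**What to change.** For Aim B1, classify IPA a second time with both GM routes removed from criterion 1: proven IPA, or Aspergillus culture plus criteria 2 to 4, among patients with a culture result. Report GM accuracy against this reference beside the Table 1 result. Label the Table 1 specificity and PPV as subject to incorporation bias. State the index cut-off and the share of patients whose GM result played both roles. Say that neither result is the true accuracy.

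The cost is one extra classification rule on culture and routine GM data that the eCRF already collects. The culture-led reference has its own weaknesses:

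- **Fewer positives.** Reference positives fall to 0.1×0.5 + 0.9×0.03 = 7.7%, against 22.2% under Table 1 in the central case, so about 35% (42%) are kept. At the same proportion, sensitivity intervals are about 1/√0.35 = 1.7 (1.5) times as wide.
- **Understated sensitivity.** A true 60%/90% test would appear as 0.0327/0.077 = 42% sensitivity and 87% specificity (50% and 85%). If GM is positive in 30-50% of culture-positive patients without IPA, sensitivity appears as 49.5-56.5% (54-58%).
- **Possible selection.** Study culture is conditional: "If available at the participating site, respiratory samples should be cultured on sabouraud-dextrose-agar". Restricting the analysis to cultured patients loses some and may select.

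These limits are the reason to show both results rather than replace one with the other.
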